7.4.2 Premedication Other than Dexamethasone for Hypersensitivity Reactions

A by-subject listing of pre-medication for elotuzumab, other than dexamethasone, will be provided. This listing will be generated from the “Pre-medication for Elotuzumab (other than Dexamethasone)” eCRF module and pre-medications will be coded using the BMS WHO drug dictionary.

7.4.3 Concomitant Medication

Concomitant medications are medications, other than study medication or pre-medications for elotuzumab recorded on the “Pre-medication for Elotuzumab” eCRF page, which are taken by subjects any time on-study, no earlier than the first day of study drug and no later than 60 days after the last dose of study drug. Concomitant medications will be coded using the BMS WHO drug dictionary. If there is clear evidence to suggest that the medication stopped prior to the first dose of study medication, the medication will be assumed to be ‘Prior’ only.

The number and percentage of subjects taking any concomitant medication and each medication (Anatomical Therapeutic Chemical [ATC] classification system drug name) will be summarized, overall and by treatment group.

A by subject listing of concomitant medication will be provided.

7.4.4 Discontinuation of Study Therapy

The number and percentage of subjects who have discontinued all study treatment and reason for discontinuation will be summarized by treatment group and overall using subject status eCRF page from end of treatment. This summary, unlike other safety analyses, will include all randomized subjects and will be grouped by treatment group as randomized. This is done in order to give a full accounting of all subjects who are off study treatment, including those who were randomized but never treated.

In addition, for subjects in the Elotuzumab arm, who discontinued one drug, while continuing at least one of the other two study drugs, their reason for treatment discontinuation will be summarized based on the dose modification CRF. Subjects will be counted in this summary if there is evidence from the dosing CRF that the subject received the combination therapy in at least one cycle, followed by additional cycles, where one of the drugs in the combination was discontinued.

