4.3.3 Dose Delay or Interruption

If the dose of one drug in the regimen (ie, lenalidomide, dexamethasone or elotuzumab) is delayed or interrupted, the treatment with the other drugs may continue as scheduled. Subjects experiencing a 28 day delay in all study drugs lenalidomide, dexamethasone, and elotuzumab due to an adverse event(s) related to study treatment must be discontinued from study drug. Subjects experiencing delays unrelated to study therapy, for example due to radiation therapy may delay study treatment up to 42 days. Delays greater than 28 days must be discussed with the medical monitor.

Each cycle is 28 days. While dose delays or interruptions are permitted, the start of each cycle cannot be delayed and is fixed relative to Cycle 1 Day 1. Adjustments to the Cycle 1 Day 1 anchored schedule should not be performed. Missed doses should be skipped, not delayed, if not given within the allowed window.

Subjects may continue on study therapy even if components of the study therapy must be discontinued. For example, a subject on lenalidomide and dexamethasone may continue on study therapy even if dexamethasone must be discontinued for an adverse event. Likewise, a subject on

the investigational arm may continue on study therapy if elotuzumab must be discontinued for an adverse event or other reason. Patients are considered still on study therapy even if they continue solely on lenalidomide.

Please consult the BMS medical monitor or any questions regarding dose interruption or study therapy discontinuation.

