7.4.1.1 Duration of Study Therapy

The number of cycles of treatment received by subjects will be summarized (using n, mean, STD, median, min, max, q1 and q3) by treatment group.

The duration of each treatment (elotuzumab, dexamethasone [oral, IV, and oral and IV combined] and lenalidomide), in months, will be calculated as:

$$(date\ of\ last\ dose\ of\ the\ drug - date\ of\ first\ dose\ of\ the\ drug + 1) / 30.4375$$

Duration of each of the study treatments will be summarized by treatment group.

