The reason for dose reduction as reported by the investigator will be tabulated for all instances with a calculated reduction based on the dose modification for Lenalidomide page. A category “unknown” will be defined for all calculated reductions with no reason reported by the investigator.

A by-subject listing of dose reductions will be generated. This will include all reported reductions per investigator, regardless of whether it met the requirements for a calculated reduction.

- **Dose Interruption**

In any cycle, the Lenalidomide dose will be considered as interrupted if there is a gap of two or more days between two dosing dates within that cycle where the subject did not receive the study drug. This will be calculated based on the information from the dose modification CRF for Lenalidomide.

The number and percentage of subjects with dose interruption, with 1, 2, 3, or \geq 4 reported interruptions will be presented. For subjects with a computed interruption, their reason for interruption will be summarized from the dose modification CRF. For subjects without an available reason for interruption, the category “unknown” will be used.

Dexamethasone (IV) and Oral:

For IV dexamethasone the following summaries will be provided:

- The number of subjects with any dose delay, with 1, 2, 3, or \geq 4 reported delays, and with a reason for delay of “hematologic toxicity”, “non-hematologic toxicity”, “AE”, “dosing error” and “other”.
- The number of subjects with any reported dose omission, with 1, 2, 3, or \geq 4 reported omissions, and with a reported reason for omission of “hematologic toxicity”, “non-hematologic toxicity”, “AE”, “dosing error” and “other”.
- The number of subjects who discontinued the study drug, and reason for the discontinuation (hematologic toxicity, non-hematologic toxicity, AE, dosing error, or other).

- The number of subjects with any reduction in the dose of the drug, and with a reason for the reduction of “hematologic toxicity”, “non-hematologic toxicity”, “AE”, “dosing error”, and “other”).

For PO dexamethasone the following summaries will be produced:

- The number of subjects with any dose modification, with 1, 2, 3, or ≥ 4 reported modifications, and with a reason for the modification of “hematologic toxicity”, “non-hematologic toxicity”, “AE”, “dosing error” and “other”).

By subject listings of record of study medication for each of IV dexamethasone and PO dexamethasone will be provided.

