7.6.2 Serious Adverse Events and Adverse Event Leading to Discontinuation

Summaries of worst grade of on-study SAE, both by individual grade (1, 2, 3, 4, or 5, along with an Any Grade category) and by grade grouped as “Any, Grade 3-4 and Grade 5” will also be presented. These summaries will be repeated for:

- On-study drug-related SAEs
- On-study AEs leading to discontinuation.
- Drug related AEs leading to discontinuation

By-subject listings of SAEs and AEs leading to study drug discontinuation will be produced.

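### SAP 7.4.4 tabulates single-drug discontinuation with reasons for the elotuzumab arm only, leaving no like-for-like table by arm of permanent stopping of lenalidomide or dexamethasone

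*SAP*

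**What the plan says.** SAP 7.4.4 plans two summaries.

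- For all randomized subjects: "The number and percentage of subjects who have discontinued all study treatment and reason for discontinuation will be summarized by treatment group and overall". The reason comes from the end-of-treatment subject status page.
- For single-drug stops, the reason is taken from the dose modification page, but only "for subjects in the Elotuzumab arm, who discontinued one drug, while continuing at least one of the other two study drugs".

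Protocol 4.3.3 makes no such distinction between arms. Its general rule is "Subjects may continue on study therapy even if components of the study therapy must be discontinued", and its first example is a control-type regimen: "a subject on lenalidomide and dexamethasone may continue on study therapy even if dexamethasone must be discontinued for an adverse event". It adds: "Patients are considered still on study therapy even if they continue solely on lenalidomide".

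Three other SAP sections bear on the point. Section 7.4.1.1 states: "Duration of each of the study treatments will be summarized by treatment group". Section 7.4.1.2 defines reductions and interruptions for lenalidomide, gives a discontinuation count with reasons for IV dexamethasone, and for oral dexamethasone starts from "The number of subjects with any dose modification". Section 7.6.2 repeats its graded summaries for "On-study AEs leading to discontinuation".

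**The concern.** The trial adds elotuzumab to a backbone that both arms receive. A basic tolerability question is whether the addition changes how often lenalidomide or dexamethasone is given up for good, and why. That needs the same count, with reasons, in both arms.

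The all-treatment table does not supply it. A subject enters that table only when the last remaining drug is stopped, and E-Ld has one more drug than Ld. Protocol 3.5 shows how this can operate: after certain severe lenalidomide reactions, subjects in the elotuzumab arm may continue the other two drugs. A control subject who gives up dexamethasone early for toxicity, stays on lenalidomide, and stops at progression much later would be expected to appear in that table once, with progression as the reason. The same history in E-Ld would also appear in the single-drug table, with its own reason.

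**Working it through.** The plan states no figure here to reproduce, so the check is mainly of which planned summary would show a control subject's permanent stop of one drug.

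**1. Summaries side by side**

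| SAP section | Arms | Permanent stop of one drug in control |
|---|---|---|
| 7.4.4, all treatment | Both, with reasons | Not counted until every drug is stopped |
| 7.4.4, single drug | E-Ld only, with reasons | Not covered |
| 7.4.1.2, lenalidomide | By treatment group for reductions | A reduction compares successive administered doses. An interruption needs a gap between two dosing dates in one cycle. A stop with no later dose meets neither definition |
| 7.4.1.2, IV dexamethasone | Discontinuation count with reasons | Control is scheduled for oral dexamethasone only (SAP 6.2) |
| 7.4.1.2, oral dexamethasone | Any modification, with reasons | Discontinuation is not separated from other modifications |
| 7.4.1.1, duration per drug | By treatment group | Reflected in duration, without reasons and mixed with progression and death |
| 7.6.2, AEs leading to discontinuation | By regimen received (7.6) | Included only if stopping any one drug counts, which is not stated |

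**2. Does relative dose intensity (7.4.1.3) fill the gap?**

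Planned lenalidomide intensity is 25 mg × 21 days / 4 weeks = 131.25 mg/week, which matches the SAP. Take a subject who receives two full cycles and then stops lenalidomide for good.

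- Cumulative dose: 2 × 21 × 25 = 1,050 mg.
- Denominator: it ends 28 days after the first dose in the last cycle with lenalidomide, so 28 + 28 = 56 days.
- Dose intensity: 7 × 1,050 / 56 = 131.25 mg/week.
- Relative dose intensity: 131.25 / 131.25 = 100%.

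The permanent stop leaves no trace. The dexamethasone denominators are cut off in the same way within each of their three periods.

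**3. How the number of drugs enters the count**

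The documents give no stopping rates, so this is illustration only. Assume each drug is stopped with the same probability p, independently of the others. With k drugs (2 in Ld, 3 in E-Ld), P(all stopped) = p^k and P(at least one stopped) = 1 − (1 − p)^k.

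| p (assumed) | All stopped, Ld / E-Ld | At least one stopped, Ld / E-Ld |
|---|---|---|
| 0.10 | 1.0% / 0.1% | 19.0% / 27.1% |
| 0.20 | 4.0% / 0.8% | 36.0% / 48.8% |
| 0.30 | 9.0% / 2.7% | 51.0% / 65.7% |
| 0.40 | 16.0% / 6.4% | 64.0% / 78.4% |

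With identical tolerability per drug, the two measures rank the arms in opposite order. The assumptions drive the size of the gap:

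- Let q be a common probability of stopping everything together, for example at progression. Then P(all stopped) = q + (1 − q)p^k. For q = 0.30 and p = 0.30 this is 36.3% versus 31.9%. For q = 0.50 and p = 0.10 it is 50.5% versus 50.05%.
- If stopping is fully dependent across drugs, the gap is zero.
- If p were 0.20 in Ld but 0.40 in E-Ld, all-stopped would be 4.0% versus 6.4%, with E-Ld the higher.

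**The case against.** The strongest reply is that the arms are compared on more than stopping everything. Duration of each drug is summarised by treatment group, so a difference in how long lenalidomide or dexamethasone is kept would show. Lenalidomide reductions are also given by treatment group. AEs leading to discontinuation are tabulated by regimen received and may already include single-drug stops: SAP 7.4.1.2 speaks of discontinuing study drug when it means IV dexamethasone alone, and Protocol section 4 counts every protocol-specified product as study drug. The table is descriptive, and it could be built later from data in hand.

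Most of this stands, and it limits what can be claimed. A reader might infer that the arms are compared on nothing but stopping all treatment, or that the planned tables can say nothing about backbone stopping. The duration and AE summaries rule out both readings. A reader might also infer that the all-treatment table makes E-Ld look better tolerated than it is. The documents do not support that as a fact. They give no per-drug stopping rates, progression ends all drugs in both arms (Protocol 3.5) and dilutes any gap, and the order can go either way.

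What remains is narrower. Duration carries no reasons. The AE table covers AE reasons only, is not planned by drug, and leaves its key term open. Neither replaces the missing control column.

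**Conclusion.** The point holds as a minor reporting gap. SAP 7.4.4 limits single-drug discontinuation with reasons to one arm, although the protocol allows the same event in both. The only discontinuation table with reasons that clearly covers both arms rests on an outcome that takes three stops in E-Ld and two in Ld, so it is not like-for-like.

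The size and direction of any distortion cannot be derived from the documents. The figures above rest on assumed rates and independence, and show only that the number of drugs can move the count. No primary or key secondary analysis, power figure or significance level is affected.

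**What to change.** In SAP 7.4.4, replace the single-arm summary with one by treatment arm, with reasons, from the dosing and dose-modification CRF pages:

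- permanent discontinuation of each drug (lenalidomide; dexamethasone, oral and IV combined; elotuzumab in E-Ld only), whether or not other drugs continue;
- permanent discontinuation of at least one drug.

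The lenalidomide and dexamethasone rows are the like-for-like comparison. The at-least-one row still spans three drugs against two and should carry a note saying so. Splitting each drug's count into stops with another drug continuing and stops of everything together would keep progression apart from single-drug toxicity.

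In SAP 7.6.2, state whether an AE leading to discontinuation means that any drug or all drugs were stopped.

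The cost is SAP wording and additional table rows and columns. No new data collection is apparent, since the SAP already uses these records for lenalidomide and dexamethasone modifications. No downside was identified.

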7.4.5 Subsequent Anti-Myeloma Therapies

The number and percentage of subjects with any subsequent systemic anti-myeloma therapy (2nd line), reason for first subsequent systemic anti-myeloma therapy regimen (Documented progression of disease, Clinical deterioration without documented progression, Maintenance therapy without disease progression or clinical deterioration, Consolidation without documented disease progression or clinical deterioration, or Other) and all subsequent systemic anti-myeloma therapy agents given categorized using the BMS WHO drug dictionary will be presented by treatment group.

The number and percentage of subjects with any second subsequent systemic anti-myeloma therapy (3rd line) and reason for second subsequent systemic anti-myeloma therapy regimen (Documented progression of disease, Clinical deterioration without documented progression, Maintenance therapy without disease progression or clinical deterioration, Consolidation without documented disease progression or clinical deterioration, or Other) will be presented by treatment group.

The number and percentage of subjects with any subsequent surgery, type of first subsequent surgery (Kyphoplasty, Orthopedic surgery, Debulking surgery or Other) will be presented by treatment group.

The number and percentage of subjects with any subsequent radiation therapy will be presented by treatment group.

A by-subject listing of all subsequent surgery, radiation therapy, and systemic anti-myeloma therapy will be provided.

7.5 Efficacy

Efficacy analyses (PFS, ORR and OS) will be conducted on the population of all randomized subjects, grouped by arm assigned at randomization, unless otherwise noted.

The main analyses of PFS and ORR will be based on IRC evaluation. Unless stated otherwise, whenever a stratified analysis is specified, the stratifications factors will be those used in the randomization (per IVRS), that is:

- Stage of disease (ISS 1 – 2 versus 3)
- Age (< 75 years old versus \geq 75 years old)
- ECOG Performance status (0 versus 1 - 2)

All p-values reported will be two-sided. Confidence intervals (CI) for the PFS and OS endpoints will be based on the nominal significance level adjusted for the interim analyses to preserve the overall type I error rate. Two-sided 95% CI will also be provided. CIs for the other endpoints will be at the two-sided 95% level. The p-values presented in the clinical study report will be rounded to the fourth decimal place. Point estimates and confidence bounds for efficacy variables will be rounded to the second decimal place.

7.5.1 Primary Analysis of Progression-Free Survival

The primary analysis of PFS will be to compare the two treatment arms via a two-sided stratified log-rank test. The primary definition of PFS using IRC assessments will be used in this analysis. The stratification factors will be the same as those used in the randomization. The two-sided log-rank p-value will be reported. An O'Brien and Fleming α spending function will be employed to determine the significance levels and stopping boundaries at the interim and final looks (see [Section 5](#) for more details).

Further analysis of PFS will include estimation of the hazard ratio and estimation of the PFS distribution in each treatment group.

The estimate of the PFS hazard ratio, of E-Ld to Ld, will be calculated using a stratified Cox proportional hazards model, with the stratification factors used at randomization and treatment as the sole covariate. Ties will be handled using the Breslow method¹¹. Two-sided, $100 * (1-\alpha)$ (α adjusted for the interim analysis) and 95% CI for the hazard ratio will also be presented.

The PFS function for each treatment arm will be estimated using the KM product limit method and will be displayed graphically. A two-sided 95% CI for median PFS in each arm will be computed via the Brookmeyer Crowley method. Estimates for 1, 2, 3, 4 and 5-years PFS rates when appropriate will be presented along with their associated 95% CIs. These estimates will come from the KM curve and their standard errors (SEs), for use in constructing CIs, will be computed using Greenwood's formula¹² and log-log transformation applied on the survivor function.

The method of Gail and Simon¹³ will be used to test for a qualitative interaction between treatment and strata, stage of disease (ISS 1 – 2 versus 3), age (< 75 years old versus \geq 75 years old) and ECOG Performance status (0 versus 1 – 2). This test will be conducted at the $\alpha=0.10$ level.

The proportional hazards assumption will be assessed via the following hazard rate model, which contains a time dependent covariate:

$$\lambda(t, z) = \lambda_i(t)e^{(b_1+b_2 \times [\log(t)] \times Z)}, \quad i = \{1 - 8\}$$

where $i=1-8$ corresponds to each of the eight levels the stratum can take, and Z is the treatment indicator, which is equal to 1 for the experimental combination arm and 0 for the control arm. The transformation of time that will be used is $\log(t)$. The null hypothesis, that the proportional hazards assumption is valid, i.e., that $b_2=0$, will be tested against the alternative hypothesis that $b_2 \neq 0$ using a Wald statistic.

[REDACTED]

[REDACTED]

[REDACTED]

[REDACTED]

[REDACTED]

[REDACTED]

[REDACTED]

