5 SAMPLE SIZE AND POWER

The number of events and power for PFS were calculated assuming an exponential distribution for each arm. One interim analysis of PFS is planned, and will allow for early stopping for superiority. An O'Brien and Fleming α spending function will be employed to determine the stopping boundaries.

Approximately 750 subjects will be randomized to the two treatment groups in a 1:1 ratio in order to obtain at least 482 progression events i.e. documented progressions or deaths. Four hundred and eighty-two events ensures that a two-sided 5% level sequential test procedure with one interim analysis will have 90.5% power if the median PFS times in the control and experimental arms were 25 and 33.75 months respectively; i.e. if the hazard ratio (HR) of the experimental arm to the control arm is 0.74.

The interim analysis of PFS will be conducted after 70% of the total events (i.e., at least 338 of the planned 482 events) have been observed.

Assuming an accrual rate of 24 subjects per month, it will take approximately 60 months to obtain the required number of events; 31 months of accrual and 29 months for PFS follow-up. At the time of final PFS analysis, an observed HR of 0.84 or less (which corresponds to a 4.8 months or greater improvement in median PFS (25 vs 29.8 months), would result in a statistically significant difference between the two treatment arms.

Survival, a key secondary endpoint, will be formally compared between the two arms at the time both ORR and PFS analyses are positive (whether that occurs after 70% of PFS events or all 482 events) and again after at least 354 deaths have been observed, which is expected to occur 7 years (84 months) after the initiation of the study. An O'Brien and Fleming α -spending function will be used to obtain the nominal significance level for the interim and final analysis of survival. Three hundred and fifty-four deaths ensure that a two-sided, $\alpha=0.05$ level test procedure with one interim analysis will have 80% power to detect a 8.7 percentage point improvement in the 4-year survival rate¹ (from 59% to 67.7%, i.e. a HR= 0.74).

Power calculations were performed using East v5.1.

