8.5 Day Conversion of Date Imputation

Conversion from days to months or years:

- 1 year = 365.25 days
- 1 month = 30.4375 days

Imputation for partial or missing progression dates:

- If only the day is missing, the 1st of the month will be used to replace the missing day.
- If the day and month are missing or a date is completely missing, the date of progression will be moved back to the last complete tumor assessment date.

In both the cases given above, the imputed date will still be considered an event.

Imputation for partial or missing death dates:

- If only the day is missing, the later of the last known alive date and the 1st of the month will be used to replace the missing day.
- If both the day and the month are missing, the later of the last known alive date and Jan 1st will be used to replace the missing information.

In both the cases given above, the imputed date will still be considered an event.

For partial dates of start of subsequent anti-myeloma therapy, the following conventions will be used:

- When the day is missing, the alternative therapy will be assumed to start on the first day of the given month if this day is later than the last dosing date. Otherwise the alternative therapy will be assumed to start on the day following the last dosing date.
- When the day and the month are missing, the alternative therapy will be assumed to start on the first day of the given year if this day is later than the last dosing date. Otherwise the alternative therapy will be assumed to start on the day following the last dosing date.

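### As printed in SAP 7.5.1, the proportional-hazards check attaches treatment only to the log-time term, so its null b2 = 0 means no treatment effect rather than proportional hazards

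*SAP*

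**What the plan says.** The check is in SAP 7.5.1, after the log-rank test, the Cox hazard ratio and the Kaplan-Meier estimates: "The proportional hazards assumption will be assessed via the following hazard rate model, which contains a time dependent covariate". The hazard in stratum i is given as λ_i(t) × exp(b1 + b2 × [log(t)] × Z), for i = 1 to 8. The bracket that opens before b1 closes after Z, so Z multiplies the log-time term only.

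The text after the formula defines Z as "the treatment indicator, which is equal to 1 for the experimental combination arm and 0 for the control arm". It then sets the hypothesis: "The null hypothesis, that the proportional hazards assumption is valid, i.e., that $b_2=0$, will be tested" with a Wald statistic.

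No significance level is given for this test. SAP 7.5 says only that "All p-values reported will be two-sided". SAP 7.5.1 does not give the unit of t either. SAP 8.4 computes PFS and OS durations from dates in days, SAP 8.5 converts with "1 month = 30.4375 days", and SAP 5 quotes PFS medians in months. SAP 7.5.9 repeats all the 7.5.1 analyses for overall survival.

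**The concern.** A proportional-hazards test of this kind needs two treatment terms: one for a constant log hazard ratio and one for its drift with log time. Zero drift is the null. The printed formula has only the drift term, so the formula and the sentence interpreting b2 = 0 cannot both be right.

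If the formula were programmed as printed, a drug with a perfectly constant benefit could be reported as showing non-proportional hazards simply because it works. Readers of the study report might then doubt the Cox hazard ratio without cause.

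**Working it through.** **1. What each form implies.** With Z = 1 against Z = 0 in the same stratum:

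- Printed: HR(t) = exp(b2 × log t) = t^b2. The factor exp(b1) applies to both arms, cancels from the partial likelihood and cannot be estimated. HR is forced to 1 at t = 1. At b2 = 0, HR is 1 at all times.
- Intended, (b1 + b2 × log t) × Z: HR(t) = exp(b1) × t^b2. At b2 = 0, HR is exp(b1), constant and free to differ from 1.

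Only the second form makes b2 = 0 equivalent to proportional hazards. This step needs no simulation.

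**2. Dependence on the time unit.** Replace t by k × t, so that log t becomes log k + log t. In the intended model the extra term b2 × log k × Z is absorbed by b1 × Z, and the test of b2 is unchanged. The printed model has no Z term to absorb it, so its result changes with the unit.

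**3. Inputs.** From SAP 5: 750 subjects randomized 1:1, 482 events, exponential PFS in each arm, 24 subjects accrued per month, and the design effect "if the median PFS times in the control and experimental arms were 25 and 33.75 months respectively". The ratio is 25/33.75 = 0.7407, stated as 0.74. There are eight strata (2 × 2 × 2). Exponential arms make proportional hazards exactly true. Assumed, because not stated: a two-sided 5% level (|z| > 1.96), with t in days, weeks, months or years.

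**4. The plan's own figures.** The fixed-design power for 482 events follows from √(482/4) × |ln 0.7407| = 10.98 × 0.300 = 3.29, giving Φ(3.29 − 1.96) = 90.9%. With one O'Brien-Fleming look at 338 events, the sequential power is 90.5% at 0.7407 and 90.7% at 0.74, against 90.5% stated. The final level comes out at 0.0455, as stated. The interim level is 0.0149 at 338/482 and 0.0148 at exactly 70%, against 0.0148 stated. The inputs therefore reproduce the design.

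**5. Simulation.** Each setting had 3,000 trials with uniform accrual, a control median of 25 months and the data cut at the target number of events. A stratified Cox model was fitted with log(t) × Z alone (printed) and with Z plus log(t) × Z (intended). The table shows the percentage of trials in which the Wald test rejects b2 = 0, although proportional hazards is true in every row. The last column is the ordinary Wald test of treatment in the same trials.

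| True HR, events | Printed, days | Printed, weeks | Printed, months | Printed, years | Intended | Treatment test |
|---|---|---|---|---|---|---|
| 0.74, 482 | 89.3 | 88.2 | 84.5 | 4.4 | 4.1 | 90.0 |
| 0.74, 338 | 77.5 | 75.0 | 68.3 | 13.7 | 4.4 | 78.6 |
| 0.70, 482 | 96.7 | 96.0 | 94.4 | 5.0 | 4.7 | 96.8 |
| 0.80, 482 | 66.5 | 64.4 | 59.3 | 4.9 | 4.5 | 67.8 |
| 0.84, 482 | 45.4 | 43.9 | 39.7 | 4.4 | 4.1 | 47.1 |
| 1.00, 482 | 4.5 | 4.7 | 5.1 | 4.6 | 4.6 | 4.4 |

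The Monte Carlo standard error is at most √(0.25/3000) = 0.9 points. In the first row, the months figure becomes 84.8% with prognostic strata and 84.9% with an assumed dropout hazard of 0.005 per month. A second run of 1,500 trials per setting gave 84% in months, 89% in days, 5% in years and 68% in months at 338 events, with about 5–6% for the intended model.

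**6. Reading the table.** In days, weeks or months, log t is positive for nearly all events, so b2 follows the treatment effect and the printed test behaves much like the treatment test. In years, log t changes sign at 12 months, early and late events pull b2 in opposite directions, and the signal largely cancels.

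**The case against.** The strongest reply is that nothing is wrong with the plan beyond a bracket, and perhaps not even that. The outer brackets are redundant as printed, which suggests that one closing bracket was displaced. That could have happened when the PDF was read: the lenalidomide dose-intensity formula in SAP 7.4.1.3 also has a bracket that closes too early. The prose, with b2 = 0 standing for proportional hazards, fits only the intended form. A programmer who tried to estimate b1 as printed would find that it cannot be done and would probably fit Z and Z × log(t).

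Most of this stands. The intent is clear, and the intended test holds its level. An extraction fault cannot be ruled out from the text alone. Nor can a misprint: the weighted response-rate difference in SAP 7.5.5 sums over 12 strata where 7.5.1 has eight. A look at the source page settles it. Clear intent does not make the printed formula a valid test.

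Two stronger readings are tempting, and the documents do not support them. A reader might infer that the check would reject true proportional hazards 85% of the time whatever the circumstances. That figure needs t in months, HR 0.74, 482 events and a 5% level, and the SAP fixes neither the unit nor the level. A reader might also infer that the reported hazard ratio or the primary result is undermined. The primary test is the stratified log-rank test, and the Cox estimate and its intervals are specified without any condition on this check. No visible text acts on a significant b2. Text after this point is blacked out, so any further use of the diagnostic cannot be judged.

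**Conclusion.** The point holds as a minor error in a prespecified diagnostic, provided the source page prints the exponent as shown. Taken literally, the test of b2 = 0 is a test of no treatment effect under an odd time-weighted model, contrary to the stated null. That conclusion is algebraic and rests on no assumption.

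The size does rest on assumptions. At a two-sided 5% level, with a constant HR of 0.74 and 482 events, false rejection of proportional hazards is about 85% with t in months, 89% in days and about 5% in years; in months at 338 events it is 68%. The intended model gives about 5%. The low figure in years does not rescue the printed form, which still has no constant-effect term and still changes its answer with the unit.

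The effect is confined to the diagnostic for PFS and, through SAP 7.5.9, for OS. No rejection rate was computed for OS, whose final analysis has 354 deaths. The stratified log-rank test and its type I error are untouched.

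**What to change.** Check the formula on the source page of SAP 7.5.1. If the closing bracket already stands before Z, nothing needs to change. If it is printed as here, correct the exponent to (b1 + b2 × log(t)) × Z, that is, a stratified Cox model with covariates Z and Z × log(t), and test b2 = 0. It would help to state the significance level of this Wald test in the same edit; the time unit then no longer matters. SAP 7.5.9 inherits the correction for OS.

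The cost is one bracket and, if wanted, one short phrase. No data collection, sample size, boundary or primary analysis changes.
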